- j) Assessments during follow up are made every 8-12 weeks, according to investigator's criteria.
- k) A serum or urine pregnancy test will be performed at the Screening Visit, at the Baseline Visit (or within 72 hours prior to the first dose of study medication)
- l) Screening tumor assessments using CT of the chest/abdomen/pelvis and other areas of known disease or newly suspected disease should be performed within 28 days prior to C1D1. Scans of the abdomen, pelvis and other areas of the body may be done with MRI instead of CT, but evaluation of the chest should be done with CT. CT scans should be performed with oral and iodinated IV contrast and MRI scans with IV gadolinium chelate unless there is a medical contraindication to contrast. If iodinated IV contrast is contraindicated, chest CT should be done without IV contrast.
- m) Somatostatin receptor scintigraphy (octreoscan) or PET-CT should be performed and/or available within the previous 6 months before C1D1, only on cohort 1-3. It is not applicable on

Clinical Study Protocol
Drug Substance DURVALUMAB/TREMELIMUMAB
Study Number ESR 15-11561-61-DUNE
EudraCT Nº: 2016-002858-20
Edition Number: 5.0 dated on June 09th, 2021

cohort 4.

- n) Survival data will be collected every 4 weeks until end of treatment phase is declared. All anticancer therapies will be collected. Survival data and other cancer treatments received will be collected every 6 months until close of the study database. The study sponsor may elect to discontinue survival follow-up.
- o) Collection of blood sample to obtain plasma, serum, or other components to be used for biomarker studies. Samples will be obtained at baseline, Cycle 2/Day 1, and at end-of-treatment visit.
- p) All subjects will have collection of most recent archived, tumor-biopsy sections for identification of predictive biomarkers.
- q) Throughout the study from the signature of Informed Consent. SAE irrespective of relationship to study treatment must be reported as soon as possible but not later than one business day. AEs and concomitant meds collected 28 days from last dose.
- r) See section 8.1.3, APPENDIX 2 and APPENDIX 3.
- s) See section 8.1.3, APPENDIX 2 and APPENDIX 3.

LIST OF TABLES

¡Error! Marcador no definido.

LIST OF APPENDICES	23
ABBREVIATIONS AND DEFINITION OF TERMS	24
1. INTRODUCTION	28
1.1 Disease Background	28
1.1.1 Immunotherapies	30
1.1.2 Durvalumab	30
1.1.3 Tremelimumab	31
1.1.4 Durvalumab in combination with tremelimumab	31

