2. STUDY OBJECTIVES

2.1 Primary objective(s)

The study will include patients with advanced neuroendocrine neoplasms in four different cohorts with the following primary endpoints:

Primary endpoint for cohorts 1, 2 and 3:

Nine-months clinical benefit rate (CBR) by Response Evaluation Criteria In Solid Tumors (RECIST 1.1), which is defined as the percentage of patients achieving complete response (CR), partial response (PR), or stable disease (SD) at month 9 after durvalumab plus tremelimumab was started.

Primary endpoint for cohort 4:

Nine-months overall survival rate, which is defined as the percentage of patients alive at month 9 after durvalumab plus tremelimumab was started.

Clinical Study Protocol
 Drug Substance DURVALUMAB/TREMELIMUMAB
 Study Number ESR 15-11561-61-DUNE
 EudraCT Nº: 2016-002858-20
 Edition Number: 5.0 dated on June 09th, 2021

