4.3 Withdrawal of Subjects from Study Treatment and/or Study

Permanent discontinuation of investigational product/study treatment

An individual subject will not receive any further investigational product if any of the following occur in the subject in question:

1. Withdrawal of consent or lost to follow-up.
2. Adverse event that, in the opinion of the investigator or the sponsor, contraindicates further dosing.
3. Subject is determined to have met one or more of the exclusion criteria for study participation at study entry and continuing investigational therapy might constitute a safety risk.
4. Pregnancy or intent to become pregnant.
5. Any AE that meets criteria for discontinuation as defined in Section 10.3.
6. Grade ≥ 3 infusion reaction.
7. Subject noncompliance that, in the opinion of the investigator or sponsor, warrants withdrawal; eg, refusal to adhere to scheduled visits.
8. Initiation of alternative anticancer therapy including another investigational agent.
9. Confirmed PD by RECIST 1.1 (CT scan or MRI at 4-6 weeks that confirms progression) and investigator determination that the subject is no longer benefiting from treatment with durvalumab + tremelimumab. Patients with documented tumor progression by image (all time-points but especially at 12 weeks), the progression should be confirmed with an additional imaging test (same characteristics) within 4-6 weeks. Treatment should continue according to protocol, until disease progression is confirmed, according the aforementioned procedure.
10. No restarts are allowed after a delay of more than 12 weeks due to toxicity or more than 4 weeks of delay if **the reason is different from toxicity** without consulting the Coordinating Investigator.

Subjects who are permanently discontinued from further receipt of investigational product, regardless of the reason (withdrawal of consent, due to an AE, other), will be identified as having permanently discontinued treatment.

Subjects who are permanently discontinued from receiving investigational product will be followed for safety per Section 10.0 and Appendix 1 or 2, including the collection of any protocol-specified blood specimens, unless consent is withdrawn or the subject is lost to follow-up or enrolled in another clinical study. All subjects will be followed for survival. Subjects who decline to return to the site for evaluations will be offered follow-up by phone every **3 months as an alternative**.

Withdrawal of consent

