8.1.3 End of Treatment

End of treatment is defined as the last planned dosing visit within the 12-month dosing period. For subjects who discontinue durvalumab or tremelimumab prior to 12 months, end of treatment is considered the last visit where the decision is made to discontinue treatment. All required procedures may be completed within \pm 7 days of the end of treatment visit. Repeat disease assessment is not required if performed within 28 days prior to the end of treatment visit.

Blood samples for biomarker analysis are collected.

Assessments for subjects who have completed durvalumab and tremelimumab treatment and achieved disease control, or have discontinued durvalumab or tremelimumab due to toxicity in the absence of confirmed progressive disease are provided in APPENDIX 2.

Assessments for subjects who have discontinued durvalumab or tremelimumab treatment due to

Clinical Study Protocol
 Drug Substance DURVALUMAB/TREMELIMUMAB
 Study Number ESR 15-11561-61-DUNE
 EudraCT Nº: 2016-002858-20
 Edition Number: 5.0 dated on June 09th, 2021

confirmed PD are presented in APPENDIX 3.

All subjects will be followed for survival until the end of the study regardless of further treatments, or until the sponsor ends the study.

Follow-up period

TC/MRI every 12 weeks until progression. Monthly visits during the first 3 months after end of treatment, every 2 months until one year, and therefore every 6 months. Determinations to be done are listed in appendix 2 and 3.

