Evaluation	Time Since Last Dose							
	Day (±3)	Months (±1 week)						12 Months and every 6 Months (±2 weeks)
		30	2	3	4	6	8	
Physical examination ^a	x							
Vital signs (temperature, respiratory rate, blood, pressure, pulse)	x							

Clinical Study Protocol
 Drug Substance DURVALUMAB/TREMELIMUMAB
 Study Number ESR 15-11561-61-DUNE
 EudraCT N°: 2016-002858-20
 Edition Number: 5.0 dated on June 09th, 2021

Weight	x							
AE/SAE assessment	x	x	x					
Concomitant medications	x	x	x					
Palliative radiotherapy	As clinically indicated							
ECOG performance status ^b	x	x	x					
Subsequent anti/cancer therapy	x	x	x	x	x	x	x	x
Survival status: phone contact with subjects who refuse to return for evaluations and agree to be contacted		x	x	x	x	x	x	x (every 2 months)
Urine hCG or serum β hCG	x							
Hematology	x	x	x					
Serum chemistry	x	x	x					
Thyroid function tests (TSH, and fT3 and fT4) ^c			x					
Pharmacokinetic assessment, if applicable			x					
SPD-L1 concentration (to assess target engagement)			x					
Tumour assessment (CT or MRI)	
For subjects who continue on MEDI4736 post-confirmed progression at the investigator's discretion (following consultation with the sponsor), tumour assessments should be performed relative to the date of first infusion per SCHEDULE OF STUDY ASSESSMENTS until study drug is stopped.
 
For subjects who discontinue study drug following confirmed progression, scans should be conducted according to local clinical practice until a new treatment is started (these scans are optional).
							

^a Full physical exam

^b PS to be collected if available at the 2 monthly calls to obtain subsequent anti/cancer therapy and survival status

^c Free T3 and free T4 will only be measured if TSH is abnormal. They should also be measured if there is clinical suspicion of an adverse event related to the endocrine system.

^d For patient questionnaires different approaches based on indication and study design.

Clinical Study Protocol
Drug Substance DURVALUMAB/TREMELIMUMAB
Study Number ESR 15-11561-61-DUNE
EudraCT Nº: 2016-002858-20
Edition Number: 5.0 dated on June 09th, 2021

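### Off-treatment survival contacts are set inconsistently, and nothing requires month-9 vital status to be known before cohort 4's primary analysis

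*Protocol*

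**What the plan says.** **Endpoint.** Protocol 2.1 defines cohort 4's primary endpoint as: "Nine-months overall survival rate, which is defined as the percentage of patients alive at month 9 after durvalumab plus tremelimumab was started".

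**Survival collection.** The places that govern it are:
- Footnote n of the Schedule of Study Assessments (same text in SAP 3.5.1): "Survival data will be collected every 4 weeks until end of treatment phase is declared", followed by "Survival data and other cancer treatments received will be collected every 6 months until close of the study database" and "The study sponsor may elect to discontinue survival follow-up".
- Protocol 3.2, treatment phase: the phase ends when the last patient in the study stops drug.
- Protocol 3.2, follow-up phase: an individual patient finishes the treatment phase after 13 cycles or at progression.
- Protocol 8.1.3: clinic visits monthly for three months after treatment, 2-monthly to one year, then 6-monthly. Also: "All subjects will be followed for survival until the end of the study regardless of further treatments, or until the sponsor ends the study".
- Protocol 4.3: "Subjects who decline to return to the site for evaluations will be offered follow-up by phone every" 3 months.
- Appendices 2 and 3: survival status by phone for patients who refuse visits, by months since last dose, ending with "x (every 2 months" in a column headed 12 months and every 6 months. Footnote b of Appendix 3 refers to 2-monthly calls for later therapy and survival status.

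**Timing of the analysis.** Protocol 11.1 and SAP 3.7.2 analyse each cohort when its last patient has reached 9 months from inclusion or has progressed. Neither requires vital status at month 9 to be known.

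**The concern.** For cohort 4, vital status on one date is the whole outcome. A site holding a progressed patient cannot tell from the documents whether survival is due every 4 weeks, every 2 months or every 6 months. The answer turns on which definition of the treatment phase is used and on whether footnote n or the appendices prevail. For patients who decline visits, section 4.3 and the appendices give different intervals outright.

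If a site follows the 6-monthly rule, a patient can be known alive shortly before month 9 and not be due for contact until well after it. If the cohort is analysed in between, the primary outcome for that patient is missing. SAP 3.7.5 names only clinical benefit rate as the variable to be imputed, so it has no specific rule for unknown vital status. Each patient is worth 1/33 = 3.0 percentage points, against a hoped-for increase of 10 points.

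**Working it through.** The plan gives no figure to reproduce here. The check is calendar arithmetic, with 1 month = 30.44 days and months counted from first dose.

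**1. Which reading exposes month 9?** Month 9 is about day 274.
- Study-level end of phase: collection stays 4-weekly while anyone in the study is on drug. Nearly every cohort 4 patient is then contacted within 4 weeks of month 9.
- Section 8.1.3 visits or appendix calls: gaps of at most about 2 months in the first year off treatment.
- Section 4.3 calls (patients who decline visits only): gaps of 3 months.
- Patient-level end of phase with footnote n: gaps of 6 months. Only this reading creates a material problem.

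**2. Contact dates on the 6-monthly reading.** Assume the clock starts at the stop date, s months after first dose; the documents do not say. Contacts fall at s + 6 and s + 12.

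| Stop | s | s + 6 | s + 12 |
|---|---|---|---|
| Week 4 | 28/30.44 = 0.9 | 6.9 | 12.9 |
| Week 8 | 56/30.44 = 1.8 | 7.8 | 13.8 |
| Week 12 | 84/30.44 = 2.8 | 8.8 | 14.8 |
| Week 16 | 112/30.44 = 3.7 | 9.7 | – |
| Week 18 | 126/30.44 = 4.1 | 10.1 | – |

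Stops before month 3 have a contact before month 9 and none until s + 12. Stops at weeks 16 to 18 are contacted about a month after month 9. The wait grows again for later stops: month 8 gives month 14.

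**3. Who is affected at the cut?** If the cut is taken when the last cohort 4 patient reaches month 9, a patient enrolled e months earlier is at month 9 + e. An early stopper's status is still open only if 9 + e < s + 12, that is, e < s + 3. For stops at weeks 4 to 12 this means enrolment in the last 3.9 to 5.8 months of accrual.

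**4. How many?** Assume even accrual of 33 patients over 33 months (protocol 13.6) or 24 months (protocol 3.1, SAP 3.8.1), and exponential survival with 13% to 23% alive at month 9 (the reference rate, and that rate plus the 10-point increase, protocol 11.3). The fraction alive at contact time t is S9^(t/9).
- Week-4 stop: window 3.9 months, so 3.9 to 5.4 patients. Alive at month 6.9: 0.13^(6.92/9) = 0.21 to 0.23^(6.92/9) = 0.32. Unknown: 0.8 to 1.7.
- Week-12 stop: window 5.8 months, so 5.8 to 7.9 patients. Alive at month 8.8: 0.14 to 0.24. Unknown: 0.8 to 1.9.

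These figures suppose that every patient in the window stopped that early, so they are generous.

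**5. The progression trigger.** Read literally for a survival endpoint, progression of the last patient at the week-12 scan would allow a cut at month 2.8 for that patient. Anyone enrolled less than 9 − 2.8 = 6.2 months earlier would not have reached month 9 at all.

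**6. Leverage of one status.** Exact binomial, n = 33, against 13% and ignoring the 5-point margin: P(X ≥ 8) = 0.057 and P(X ≥ 9) = 0.022. One patient can move the result across 5%. This shows why completeness matters. It says nothing about how often status will be unknown.

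**The case against.** The strongest reply is that a sparse schedule does not lose the endpoint. SAP 3.5 records survival as a date and a status, and protocol 10.3.2.1 keeps later deaths as survival events. Any contact after month 9 therefore settles month-9 status. Protocol 13.6 leaves 24 months between last subject in (December 2019) and last visit (December 2021), against a latest contact in the table of 14.8 months. All of this stands. It confines the problem to a cut taken early, to patients lost between contacts, and to follow-up that the sponsor ends.

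The denser schedules also stand. The assessment schedule sends the reader to 8.1.3 and Appendices 2 and 3 for end of treatment and follow-up, and a site that follows them has gaps of about 2 months.

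Several stronger readings are tempting and are not supported:
- *Four rival post-treatment schedules.* The 4-weekly interval applies off treatment only under the study-level definition, and on that reading the 6-monthly gap largely disappears. The 3-monthly interval is an alternative for patients who decline visits.
- *Patients progressing at the first scan jump over month 9.* Protocol 4.3 and section 9 describe treatment continuing until progression is confirmed, absent clinically significant deterioration. With confirmation 4 to 6 weeks later, such stops fall at about weeks 16 to 18, with contact at months 9.7 to 10.1. The exposed early stops are mainly those for other reasons.
- *The sponsor may drop survival follow-up before month 9.* The option has no earliest date, but 4.3 and 8.1.3 say that all subjects are followed, and nothing suggests an intention to stop early.

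**Conclusion.** The inconsistency is real, and its effect on the primary endpoint is limited. On one reading of footnote n, late-enrolled cohort 4 patients who stop in about the first 3 months could be last contacted before month 9 and not again until about months 13 to 15. With a cut at the last patient's month 9, their status could be unknown. Under even accrual and exponential survival this is about 1 to 2 of 33 patients at most (3 to 6 points). The documents give neither a distribution of stopping times nor cohort 4's accrual pattern, so that size is an illustration.

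A reader might infer that month-9 survival cannot be ascertained in cohort 4, or that about 5 deaths would go unseen. The second figure (4.8 to 5.3) follows from 33 × the average of S(9 − u) − S(9) for u between 0 and 6 months. It puts all 33 patients at exactly month 9 on the cut date. Staggered entry rules that out, and the documents do not support either inference.

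The defect that remains is that no rule ties the cohort 4 cut to known month-9 status. The progression alternative in the trigger and the open-ended sponsor option leave that gap open.

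**What to change.** 1. Define the end of the treatment phase once for the purposes of footnote n, and state whether it is per patient or per study.
2. Use one off-treatment survival-contact interval in footnote n, sections 4.3 and 8.1.3, Appendices 2 and 3, and the SAP schedule. The 2-monthly interval already in the appendices would serve.
3. Before the cohort 4 data cut, require vital status known at or after month 9 from first dose for every cohort 4 patient, by phone or medical record.
4. Remove progression of the last patient as a trigger for the survival endpoint in protocol 11.1 and SAP 3.7.2 and 2.1.
5. State that the sponsor may not end survival follow-up before item 3 is met.

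No fixed day-274 visit is needed, because a later dated contact gives the same information. Edition 5.0 is dated June 2021, and on the protocol 13.6 timetable the last patient's month 9 fell in about September 2020. For this trial the check may therefore have to be retrospective.

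The cost is a short wording change in both documents, one call or record check per patient, and possibly a short delay of the cut.

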10.3 Recording of adverse events and serious adverse events

Adverse events will be recorded in the eCRF using a recognized medical term or diagnosis that accurately reflects the event. Adverse events will be assessed by the investigator for severity, relationship to the investigational product, possible etiologies, and whether the event meets criteria of an SAE and therefore requires immediate notification and not later than 24 h, to the Sponsor.

Clinical Study Protocol
 Drug Substance DURVALUMAB/TREMELIMUMAB
 Study Number ESR 15-11561-61-DUNE
 EudraCT Nº: 2016-002858-20
 Edition Number: 5.0 dated on June 09th, 2021

The following variables will be collected for each AE:

- AE (verbatim)
- The date when the AE started and stopped
- Changes in NCI CTCAE grade and the maximum CTC grade attained
- Whether the AE is serious or not
- Investigator causality rating against durvalumab or tremelimumab (yes or no)
- Action taken with regard to durvalumab + tremelimumab
- Outcome

In addition, the following variables will be collected for SAEs as applicable:

- Date AE met criteria for serious AE
- Date Investigator became aware of serious AE
- AE is serious due to criteria
- Date of hospitalization
- Date of discharge
- Probable cause of death
- Date of death
- Autopsy performed
- Description of AE
- Causality assessment in relation to Study procedure(s)

Events, which are unequivocally due to disease progression, should not be reported as an AE during the study.

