10.3.2.1 Reporting of deaths

All deaths that occur during the study, or within the protocol-defined 90-day post-last dose of durvalumab + tremelimumab safety follow-up period must be reported as follows:

- Death that is clearly the result of disease progression should be documented but should not be reported as an SAE.
- Where death is not due (or not clearly due) to progression of the disease under study, the AE causing the death must be reported to as a SAE within **24 hours** (see Section 10.3.2 for further details). The report should contain a comment regarding the co-involvement of progression of disease, if appropriate, and should assign main and contributory causes of death.
- Deaths with an unknown cause should always be reported as a SAE.

Deaths that occur following the protocol-defined 90-day post-last-dose of durvalumab safety follow-up period will be documented as events for survival analysis, but will not be reported as an SAE.

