10.3.3 Other events requiring reporting

10.3.3.1 Overdose

An overdose is defined as a subject receiving a dose of durvalumab + tremelimumab in excess of that specified in the Investigator's Brochure, unless otherwise specified in this protocol.

Any overdose of a study subject with durvalumab + tremelimumab, with or without associated AEs/SAEs, is required to be reported within 24 hours of knowledge of the event to the sponsor, who will send a copy to [REDACTED] Patient Safety, or designed using the designated Safety e-mailbox (see Section 10.3.2 for contact information). If the overdose results in an AE, the AE must also be recorded as an AE (see Section 10.3). Overdose does not automatically make an AE serious, but if the consequences of the overdose are serious, for example death or hospitalization, the event is serious and must be recorded and reported as an SAE (see Section 10.3 and Section 10.3.2). There is currently no specific treatment in the event of an overdose of durvalumab or tremelimumab.

The investigator will use clinical judgment to treat any overdose.

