10.3.3.2 Hepatic function abnormality

Hepatic function abnormality (as defined in Section 10.1.3.) in a study subject, with or without associated clinical manifestations, is required to be reported as "hepatic function abnormal" **within 24 hours of knowledge of the event** to the sponsor, who will send a copy to [REDACTED] Patient Safety, using the designated Safety e-mailbox (see Section 10.3.2 for contact information), unless a definitive underlying diagnosis for the abnormality (e.g.,

Clinical Study Protocol
 Drug Substance DURVALUMAB/TREMELIMUMAB
 Study Number ESR 15-11561-61-DUNE
 EudraCT Nº: 2016-002858-20
 Edition Number: 5.0 dated on June 09th, 2021

cholelithiasis or bile duct obstruction) that is unrelated to investigational product has been confirmed.

- If the definitive underlying diagnosis for the abnormality has been established and is unrelated to investigational product, the decision to continue dosing of the study subject will be based on the clinical judgment of the investigator.
- If no definitive underlying diagnosis for the abnormality is established, dosing of the study subject must be interrupted immediately. Follow-up investigations and inquiries must be initiated by the investigational site without delay.

Grade 1-2 events should be considered AEs, not SAEs. However, Grade 1-2 events should be reported as SAEs if requires hospitalization or if they are medically important events based on the investigator judgement.

Grade 3 events, should be reported as SAE if requires hospitalization or if they are medically important events based on the investigator judgement.

All grade 4 events should be reported as SAEs.

Cases where a patient shows elevations in liver biochemistry may require further evaluation and occurrences of AST or ALT $\geq 3 \times$ ULN together with total bilirubin $\geq 2 \times$ ULN may need to be reported as SAEs.

Each reported event of hepatic function abnormality will be followed by the investigator and evaluated by the sponsor.

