10.3.3.3 Pregnancy

a) Maternal exposure

If a patient becomes pregnant during the course of the study, the IPs should be discontinued immediately.

Pregnancy itself is not regarded as an AE unless there is a suspicion that the IP under study may have interfered with the effectiveness of a contraceptive medication. Congenital abnormalities or birth defects and spontaneous miscarriages should be reported and handled as SAEs. Elective abortions without complications should not be handled as Aes. The outcome of all pregnancies (spontaneous miscarriage, elective termination, ectopic pregnancy, normal birth, or congenital abnormality) should be followed up and documented even if the patient was discontinued from the study.

If any pregnancy occurs in the course of the study, then the Investigator or other site personnel should inform the appropriate sponsor representatives within 1 day, ie, immediately, but **no later than 24 hours** of when he or she becomes aware of it.

The designated sponsor representative will work with the Investigator to ensure that all relevant information is provided to the sponsor, who will inform [REDACTED] Patient Safety data entry site. The same timelines apply when outcome information is available.

b) Paternal exposure

Male patients should refrain from fathering a child or donating sperm during the study and for 180 days after the last dose of durvalumab + tremelimumab combination therapy or 90 days after the last dose of durvalumab monotherapy, whichever is the longer time period.

Clinical Study Protocol
 Drug Substance DURVALUMAB/TREMELIMUMAB
 Study Number ESR 15-11561-61-DUNE
 EudraCT N°: 2016-002858-20
 Edition Number: 5.0 dated on June 09th, 2021

Pregnancy of the patient's partner is not considered to be an AE. However, the outcome of all pregnancies (spontaneous miscarriage, elective termination, ectopic pregnancy, normal birth, or congenital abnormality) occurring from the date of the first dose until 90 days after the last dose should, if possible, be followed up and documented.

Where a report of pregnancy is received, prior to obtaining information about the pregnancy, the Investigator must obtain the consent of the patient's partner. Therefore, the local study team should adopt the generic ICF template in line with local procedures and submit it to the relevant Ethics Committees (ECs) prior to use.

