- k) A serum or urine pregnancy test will be performed at the Screening Visit, at the Baseline Visit (or within 72 hours prior to the first dose of study medication).
- l) Screening tumor assessments using CT of the chest/abdomen/pelvis and other areas of known disease or newly suspected disease should be performed within 28 days prior to C1D1. Scans of the abdomen, pelvis and other areas of the body may be done with MRI instead of CT, but evaluation of the chest should be done with CT. CT scans should be performed with oral and iodinated IV contrast and MRI scans with IV gadolinium chelate unless there is a medical contraindication to contrast. If iodinated IV contrast is contraindicated, chest CT should be done without IV contrast.
- m) Somatostatin receptor scintigraphy (octreoscan) or PET-CT should be performed and/or available within the previous 6 months before C1D1.
- n) Survival data will be collected every 4 weeks until end of treatment phase is declared. All anticancer therapies will be collected. Survival data and other cancer treatments received will be collected every 6 months until close of the study database. The study sponsor may elect to discontinue survival follow-up.
- o) Collection of blood sample to obtain plasma, serum, or other components to be used for biomarker studies. Samples will be obtained at baseline, Cycle 2/Day 1, and at end-of-treatment visit.
- p) All subjects will have collection of most recent archived, tumor-biopsy sections for identification of predictive biomarkers.
- q) Throughout the study from the signature of Informed Consent. SAE irrespective of relationship to study treatment must be reported as soon as possible but not later than one business day. AEs and concomitant meds collected 28 days from last dose.

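### Footnote q of the protocol schedule allows one business day to report an SAE while section 10.3 allows 24 hours, so a report made after a weekend can satisfy one text and breach the other

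*Protocol*

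**What the plan says.** **Protocol, schedule of study assessments, footnote q** (attached to the AEs/SAEs row). An SAE, whatever its causality, "must be reported as soon as possible but not later than one business day". The footnote names no recipient, does not define a business day and does not refer to section 10. It also limits collection of AEs and concomitant medication to 28 days from the last dose.

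**Protocol 10.3.** An event that meets the SAE criteria "requires immediate notification and not later than 24 h, to the Sponsor".

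**Protocol 10.3.2.1.** For a death that is not due, or not clearly due, to progression, "the AE causing the death must be reported to as a SAE within 24 hours".

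**Protocol 10.3.2**, the section on SAE reporting itself, gives no site-to-sponsor time limit.

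**Protocol 10.3.1** records AEs and SAEs up to 90 days after the last dose.

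**SAP 3.5.1, footnote q**, carries the schedule's wording: "SAE irrespective of relationship to study treatment must be reported as soon as possible but not later than one business day". It also repeats the 28-day AE period.

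**The concern.** Both limits govern the same act, a site telling the sponsor of an SAE, and a business day is not the same as 24 elapsed hours. The schedule is the page that site staff use visit by visit, and its footnote is worded as an obligation. A site could follow it in good faith and report after the limit in section 10.3.

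Two things are at stake. The first is the age of the information when it reaches the sponsor, whose own notices to the authorities and to the drug supplier (section 10.3.2) depend on the site's report. Such reports will not be rare: section 1.4.2.3 puts treatment-related SAEs at about 15% of patients in the pooled combination studies. The second is compliance. A monitor or auditor could not classify a report made at, say, 60 hours consistently, because the protocol gives two answers.

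**Working it through.** The plan states no figure to reproduce. The check has two parts: a comparison of all the reporting limits, and calendar arithmetic on the two that conflict.

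**1. Limits side by side**

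| Place in the protocol | What it covers | Limit |
|---|---|---|
| Schedule, footnote q | all SAEs | one business day |
| 10.3 | all SAEs | 24 h, to the sponsor |
| 10.3.2 | all SAEs | none stated for the site |
| 10.3.2.1 | deaths not clearly due to progression | 24 h |
| 10.3.3.1 | overdose | "is required to be reported within 24 hours of knowledge of the event to the sponsor" |
| 10.3.3.2 | hepatic function abnormality | "within 24 hours of knowledge of the event to the sponsor" |
| 10.3.3.3 | pregnancy | "within 1 day, ie, immediately, but no later than 24 hours" |

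Only section 10.3 conflicts with the footnote for SAEs in general. The later rows cover particular events. They show that 24 hours is the limit throughout section 10 and that the footnote is the exception.

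**2. Size of the gap**

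Assumptions, because the documents do not define the term:
- business days are Monday to Friday;
- the clock starts at site awareness;
- the deadline falls on the next business day, between the same clock time and midnight.

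Formulas: footnote limit = hours from awareness to that deadline; excess = footnote limit − 24.

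| Awareness | Footnote limit (h) | Excess over 24 h |
|---|---|---|
| Wednesday 17:00 | 24 to 31 | 0 to 7 |
| Friday 09:00 | 72 to 87 | 48 to 63 |
| Friday 17:00 | 72 to 79 | 48 to 55 |
| Saturday 12:00 | 48 to 60 | 24 to 36 |
| Sunday 12:00 | 24 to 36 | 0 to 12 |

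Example: Friday 17:00 to Monday 17:00 is 3 × 24 = 72 h, and 72 − 24 = 48 h over. Running to midnight adds 7 h, giving 79 h and an excess of 55 h.

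If Monday is a public holiday, each Friday, Saturday and Sunday row gains 24 h. Friday 17:00 becomes 96 to 103 h, an excess of 72 to 79 h.

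**3. The other mismatch in the same footnote**

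AE collection ends at 28 days in footnote q and at 90 days in section 10.3.1, a difference of 90 − 28 = 62 days. Two departures from section 10 in one footnote suggest that it was not updated with that section, rather than that it states a deliberate alternative.

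**The case against.** The strongest reply is that section 10 is the operative text. Its opening makes the principal investigator responsible for ensuring that all study staff know it, it states the sponsor as recipient, and its limits are uniform. The footnote also asks for prompt reporting, so a site that reports within 24 hours satisfies both texts. Only a site that works from the footnote alone can be late, and then materially so only for events learned of on a Friday or Saturday or before a holiday. All of this stands and limits the size of the point. It does not remove the contradiction, because no passage gives section 10 precedence.

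A reader might infer more than the documents support:

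- *That the gap undermines the first-patient safety run in each cohort.* Edition 5.0 is dated June 2021, and section 13.6 puts the last subject in at December 2019, so those decisions were past. The SAP of November 2017 shows that the footnote wording is older, but what section 10.3 then said cannot be seen. The run-in also lasts a 4-week cycle, so a delay of two or three days could matter only near its end.
- *That SAE reporting is the main safety control because there is no interim look.* SAP 3.7.6 concerns interim analyses, not safety oversight. Site-level protection acts before any notice to the sponsor (protocol 4.3, 5.2.4, 10.3.3.2 and Appendix 1), and section 14.1 describes continuing product safety monitoring.
- *That section 10.3.2.1 sets 24 hours for every SAE.* It covers only deaths not clearly due to progression.

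**Conclusion.** The inconsistency is real and in current text. Under the stated reading of a business day, a site that follows footnote q can report about 48 to 63 hours after the section 10.3 limit for an SAE learned of during Friday working hours, and 24 to 36 hours after it for one learned of at midday on Saturday. A Monday holiday adds 24 hours. For midweek awareness the excess is 0 to 7 hours in the case computed, and for Sunday midday before an ordinary Monday it is 0 to 12 hours. These sizes rest on an undefined term; a different reading of a business day would change them.

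The point still applies to edition 5.0, since section 13.6 plans the last visit for December 2021 and section 5.2.2 allows up to 12 months of retreatment. It is a documentary fault in safety reporting. It affects no endpoint, analysis, sample size, power or alpha, and it does not show that any report was in fact late.

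**What to change.** - **Protocol, footnote q:** replace the one-business-day limit with the limit in section 10.3, stated as 24 hours from site awareness and addressed to the sponsor. Alternatively, remove the limit and refer to section 10.3. Stating the clock start in section 10.3 as well would help, because that section does not give one.
- **Same edit:** reconcile the footnote's 28-day AE collection period with the 90 days in section 10.3.1. Changing only the reporting phrase would leave the footnote at odds with section 10.
- **SAP 3.5.1, footnote q:** update for consistency only. The SAP does not direct site reporting, and SAP 5.3 says that it is based on protocol version 3.1.

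The cost is a short text change in the protocol, a matching one in the SAP, and a note to sites. No visit, assessment or analysis changes as a result of aligning the reporting limit.
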